18.2 PLANNED RECRUITMENT RATE

We aimed to randomise up to 1000 patients within 24 months of recruitment. The power for the primary endpoint of time to occurrence of liver related outcomes from randomisation is sufficiently great that we will still be very well powered even if there is a substantial drop out rate of as high as 15%-20%. The recruitment target is approximately 42 patients per month. In order to randomise 1000 patients into the trial, it is estimated from previous research³⁶ that approximately 2160 patients will have to be registered to undergo screening with the ELF test (to have 1000 patients meet the randomisation inclusion criteria of $ELF \geq 8.4$).

Following the recommendation by the funding body to close the trial to recruitment, it is anticipated that by the time the resulting protocol amendment is approved and implemented, approximately 700 patients will have been randomised.

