Eligible participants will be randomised on a 1:1 ratio to the intervention (standard follow-up screening for cirrhosis plus an ELF test) or non-intervention arm (standard follow-up screening for cirrhosis) of the trial using an automated 24-hour telephone randomisation system provided by the Clinical Trials Research Unit (CTRU). If the patient is randomised to 'follow-up screening for cirrhosis with ELF test' and the ELF score indicates they are cirrhotic, the randomisation system will also notify the caller so 'management' of cirrhosis can begin. All participants will have further data collected and recorded (see section 14.2). Those patients who consented for the optional trial translational research biobank will provide a serum sample for the biobank at the randomisation visit.

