Eighty out of the first 225 (37%) patients have presented with an ELF >9.49 . We are aiming to recruit 500 patients per arm, so we would expect 185 control arm patients to have an ELF >9.49 . With a 22% incidence rate of severe complications at 36 months, 24 months of recruitment and 30 months of follow up the expected number of events in these 185 patients can be calculated, using the method described by Collett⁴⁴ for sample size estimates based on exponential survival distributions (more details of which can be seen in the SAP). This produces an estimate of 46.4 events in these 185 control arm patients. We would also expect approximately 10% of the remaining 315 control arm patients to progress to cirrhosis on clinical grounds and to subsequently have a similar probability of then developing severe complications. This adds another 5.1 estimated events from this group, giving a total of approximately 52 estimated events in the control arm. We expect to reduce this number by 40% in the ELF arm, giving a total number of estimated events in this arm of 31. The median survival times, assuming negative exponential survival distributions, that would produce these numbers of events for the control and ELF arms with 24 months of recruitment and 30 months of follow up are 22.5 and 39.1 years, respectively. These figures can be used to calculate the power to detect such an effect size, which, with a type I error rate of 5%, gives a figure of 70%. However, if follow-up is continued until five years beyond the end of the programme grant, i.e. 69 months of follow-up rather than 30, the power to detect this effect size increases to just over 90%.

To calculate the power, with these 1000 patients, to detect a difference in the secondary endpoint of numbers of patients encountering severe complications subsequent to being detected with cirrhosis, we also need to estimate the numbers of patients developing cirrhosis in the two arms. We expect approximately 10% of the 315 patients with an ELF score between 8.4 and

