Power calculations are based on our hepatology estimates of the identification of large varices in cirrhotic patients and the expected identification of cirrhotic patients in the ELF and control arms. Once identified as cirrhotic, approximately 10% of patients are predicted to be treated with beta-blockers/band ligation (BB/BL) of varices.

In the ELF arm, current estimates suggest 40% of patients will be diagnosed with cirrhosis initially, and 10% diagnosed during follow up to July 2014. Therefore in this total of 50% of patients, we would predict the use of BB/BL in 1 in 10, i.e. 5% of the total. In the control arm, conservatively we predict the clinical diagnosis of cirrhosis to be made in under 10% of the patients by July 2014: therefore 1% of the total would receive BB/BL. Based on the

assumption of 700 patients randomised at the end of the recruitment period and follow up until July 2014, power is 86%. We will have approximately 40% power for this endpoint at the interim analysis in summer 2013. Similarly with the additional follow up until July 2014, we will have good power to show changes in the frequency of endoscopy and ultrasound/AFP's to detect HCC at a surgically curable stage and also to detect changes in Liver Function Tests (LFT's) in patients with Hepatitis B and Hepatitis C. The power to detect changes in the frequency of endoscopy and ultrasound/AFP's should be very good (>90%) at the interim analysis in summer 2013, and the power to detect changes in LFTs should be of the order of 60% for Hepatitis B patients and 90% for Hepatitis C patients.

As previously mentioned we will also have enough patients to have good statistical power (approximately 80%) after five years further follow up for the detection of changes in the primary endpoints of the existing trial which are major liver events and survival. These endpoints will only be delivered with long follow up of five years. This will capture major liver events and long term consequences of ELF testing, survival and health economics.

The detailed information collected within the Programme and the impact of ELF on the process of care will provide detailed information that will be essential in the interpretation of the long follow up and the impact of ELF testing on major liver events and survival.

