19.2 STATISTICAL ANALYSIS POPULATIONS

All analyses will be conducted on the intention-to-treat (ITT) population and carried out at a 2-sided 5% level of significance. The ITT population is defined as all patients randomised to treatment regardless of non-compliance, loss to follow-up, or death.

The secondary endpoint analysis, incidence of cirrhosis in non-randomised patients, will be conducted on follow-up data from those patients who registered and consented to the trial, but who were not randomised due to having an ELF score of < 8.4 (see section 6.3).

Attempts will be made to retrieve missing data via a thorough data cleaning process.

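### Section 18.2 still promises a very well powered primary endpoint under 15–20% drop-out, but at about 700 patients the plan's own inputs give about 70–78% (69 months) or 72–83% (75–81 months)

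*Protocol*

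**What the plan says.** Section 18.2 (Planned recruitment rate) opens with the original target of 1000 patients in 24 months. It then says that power for the primary endpoint is large enough that "we will still be very well powered even if there is a substantial drop out rate of as high as 15%-20" per cent. The next paragraph of 18.2 reports the early closure and expects that "approximately 700 patients will have been randomised".

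Section 18.1 gives three power figures for time from randomisation to first severe complication:

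- 1000 patients, 24 months of recruitment and 30 months of follow-up: "which, with a type I error rate of 5%, gives a figure of 70" per cent.
- 1000 patients, 69 months of follow-up: just over 90%. On this basis section 18.1 calls the trial at its original size well powered, at 90% or more.
- About 700 patients: "good statistical power (approximately 80%) after five years further follow up".

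Drop-out appears only in section 18.2, and no power figure is attached to it.

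**The concern.** The claim of robustness rests on power being large. If the stated powers hold only with complete follow-up, they contain no reserve for losing up to one patient in five. The early closure also lowers the starting point from just over 90% to about 80%. The amendment moved neighbouring text into the past tense or tied it to the original size, but left this sentence as a statement about the current trial.

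The primary endpoint depends on long-term follow-up for which section 18.1 says funding is still being sought. The funder and the steering and monitoring committees therefore need a correct statement of how much loss the trial of about 700 can absorb.

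**Working it through.** **Inputs.** Section 18.1: exponential medians of 22.5 years (control) and 39.1 years (ELF), 24 months of recruitment, minimum follow-up of 30 or 69 months, 500 per arm ("We are aiming to recruit 500 patients per arm, so we would expect 185 control arm patients to have an ELF >9.49"). Section 18.2: about 700 patients, so 350 per arm. Section 6.2: 1:1 allocation. Section 19.2: tests "carried out at a 2-sided 5% level of significance".

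**Formulas.** With hazard λ, uniform recruitment over a = 24 months and minimum follow-up f:

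- P(event) = 1 − [exp(−λf) − exp(−λ(f+a))] / (aλ)
- Schoenfeld power = Φ(½·√E·|ln HR| − 1.96)
- Freedman power = Φ(√E·(1−HR)/(1+HR) − 1.96), where E is total events.

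**Hazards.** Control: ln 2/270 = 0.002567 per month. ELF: ln 2/469.2 = 0.001477 per month. HR = 0.575, |ln HR| = 0.5526, (1−HR)/(1+HR) = 0.2695.

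**Step 1: reproduce the plan's figures with no loss.**

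- The 185 high-ELF control patients: λ = −ln(0.78)/36 = 0.006902, f = 30, giving 46.4 events (stated 46.4).
- 1000 patients, 30 months: 51.0 + 30.1 = 81.1 events (stated about 52 and 31). Power 70.1% Schoenfeld, 68.0% Freedman (stated 70%).
- 1000 patients, 69 months: 93.8 + 56.4 = 150.2 events. Power 92.3% and 91.0% (stated just over 90%).
- 700 patients, 69 months: 65.7 + 39.5 = 105.1 events. Schoenfeld: ½·√105.1·0.5526 − 1.96 = 0.87, so 80.9%. Freedman: √105.1·0.2695 − 1.96 = 0.80, so 78.9% (stated about 80%).

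All three stated powers match with zero drop-out.

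**Step 2: apply the stated loss d = 15% or 20%.** Two models bracket the timing:

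- *At the start:* lost patients contribute nothing, so n becomes n(1−d).
- *Gradual:* exponential censoring at rate γ = −ln(1−d)/(f+12), which reaches d by mean follow-up. Then P(event) = λ/(λ+γ) times the expression above with λ+γ in place of λ.

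**Step 3: the horizon for 700 patients.** The 69 months belong to the original timetable. Randomisation closes on 30 April 2013 (section 6.2). Five years after July 2014 ends in July 2019, about 75 months after the last randomisation. Section 19.1 puts July 2014 six months before the end of the revised grant. Five years after that end is January 2020, about 81 months. Both are assumptions, because the protocol does not restate the minimum follow-up.

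Power in %, Freedman to Schoenfeld:

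| Patients, minimum follow-up | No loss | 15% at start | 20% at start | 15% gradual | 20% gradual |
|---|---|---|---|---|---|
| 1000, 69 months | 91.0–92.3 | 86.1–87.7 | 84.0–85.7 | 88.8–90.3 | 87.9–89.4 |
| 700, 69 months | 78.9–80.9 | 72.2–74.3 | 69.5–71.7 | 75.7–77.8 | 74.5–76.6 |
| 700, 75 months | 81.5–83.3 | 74.9–77.0 | 72.3–74.5 | 78.4–80.4 | 77.2–79.3 |
| 700, 81 months | 83.7–85.5 | 77.4–79.4 | 74.9–77.0 | 80.8–82.7 | 79.7–81.6 |

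Gradual loss reaching d by the minimum follow-up instead gives values between the two models.

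**The case against.** **The sentence describes the original design.** It sits in a paragraph about 1000 patients, and section 18.1 ties that design to the long horizon. There, 84–90% remains after the stated loss, so the claim was defensible when it applied. This stands. It does not rescue the present-tense wording, because that design can no longer be attained.

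**The 30-month horizon.** A reader might infer that the claim was never true, because 18.1 gives only 70% at 30 months before any loss. The documents do not support using that against this sentence. Section 18.1 discloses the 70%, says that major liver events and survival will not be reported within the programme, and makes them depend on five further years. Section 19.1 places the final primary analysis there. The 30-month figure serves here only to confirm the method.

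**Clearly below 80%.** A reader might also infer that loss takes the current trial well under 80% in every case. That holds only if 69 months is carried over. At 75–81 months some gradual-loss cases reach 80–83%.

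**Visit drop-out is not endpoint loss.** Section 11 plans to collect endpoint data on all registered patients through routine NHS sources, section 19.2 keeps all randomised patients in the analysis, and visits stop at 30 months anyway (section 14.5). Loss at the start is therefore a pessimistic bound. This is fair, but section 18.2 does not rely on it: it claims robustness because power is large.

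**Conclusion.** The point holds as a statement about the current trial. The powers in 18.1 make no allowance for loss. At about 700 patients the stated 15–20% drop-out leaves about 70–78% with 69 months of minimum follow-up, and about 72–83% with 75–81 months. Even the most favourable of these is below the 90% that 18.1 itself calls well powered, and 18.1 describes the undiminished figure of about 80% only as good.

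The result rests on the plan's medians, on 24-month uniform accrual also for the 700 patients, on drop-out meaning loss of endpoint data, and on the assumed horizon. The ranges cover both loss models and both formulas. No analysis or sample size depends on the sentence. What is wrong is a stated property of the primary comparison that the current trial does not have.

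**What to change.** In section 18.2, either limit the sentence explicitly to the original design of 1000 patients with long-term follow-up, or replace it with wording such as: *With about 700 patients and a minimum follow-up of 69 months, power for the primary endpoint is about 80% with complete endpoint ascertainment and about 70–78% if 15–20% of patients are lost to endpoint follow-up.* If a longer minimum follow-up is intended, state it and give the matching figures. In either case, remove the present-tense claims that power is sufficiently great and that the trial remains very well powered.

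The cost is a wording change and a less favourable stated figure. No design change, extra data collection or new analysis is needed.

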19 STATISTICAL ANALYSIS

The statistical analysis plan is the responsibility of the CTRU Study Statistician. The analysis plan outlined in this section is detailed further in the statistical analysis plan and will be reviewed before the final analysis is undertaken. The analysis plan will be written in accordance with current CTRU Standard Operating Procedures (SOPs) and will be finalised and agreed by the following people: the Study Statistician, the Supervising Statistician, the Chief Investigator, the CTRU Principal Investigator, and the

Senior Trial Coordinator. Any changes to the finalised analysis plan, and reasons for the changes, will be well documented.

19.1 FREQUENCY OF ANALYSIS

Interim reports will be presented to the Data Monitoring and Ethics Committee (DMEC) in strict confidence at approximately yearly intervals or as soon as sufficient data have been accrued to make them meaningful. A single formal interim analysis is planned on the primary endpoint at a time when approximately half the number of expected events will have occurred, estimated to be approximately summer 2013, roughly 27 months after the start of recruitment to version 5.0 of the protocol. This interim analysis will include the new process outcomes, where we anticipate we will have sufficient information for an informative analysis at this time. The DMEC, in the light of the interim reports and of any advice or evidence they wish to request, will if necessary report to the Trial Steering Committee (TSC) if there are concerns regarding the safety or efficacy of either of the study treatment policies.

Apart from the interim analysis to the DMEC in summer 2013, no other formal analyses are planned until 6 months prior to the end of the revised 6 years of the Programme Grant, in July 2014, close to 3 years of recruitment and follow-up. Analyses after the 6 year timescale of the Programme Grant will be considered by the TSC at a later stage, and include the final analysis of time from randomisation to incidence of first severe complication at the end of the additional 5 years of follow up.

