20 DATA MONITORING

20.1 DATA MONITORING AND ETHICS COMMITTEE

An independent Data Monitoring and Ethics Committee (DMEC) will review the safety and ethics of the study. Detailed unblinded reports will be prepared by the CTRU for the DMEC at approximately 6-12 month intervals. The formal interim analysis on the primary endpoint and on the process of care outcomes will be reported to the DMEC in summer 2013, approximately 27 months after the start of recruitment.

The DMEC will be provided with detailed unblinded reports containing the following information:

- Rates of occurrence of SAEs (see section 14)

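### The summer 2013 interim would hold about 20% of the final primary events, not half, and the two-sided 5% level is not reserved for the final analysis

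*Protocol*

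**What the plan says.** Protocol section 19.1 plans one formal interim on the primary endpoint at "a time when approximately half the number of expected events will have occurred, estimated to be approximately summer 2013", described as "roughly 27 months after the start of recruitment to version 5.0 of the protocol". The new process outcomes are included in it. The next formal analysis is in July 2014, with no endpoint named, and section 19.1 then places "the final analysis of time from randomisation to incidence of first severe complication at the end of the additional 5 years" after the Programme Grant ends. Section 20.1 repeats the plan: "The formal interim analysis on the primary endpoint and on the process of care outcomes will be reported to the DMEC in summer 2013".

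Section 19.2 sets the level: "All analyses will be conducted on the intention-to-treat (ITT) population and carried out at a 2-sided 5% level of significance". It makes no exception for the interim.

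Section 18.1 gives the rates. Exponential medians "for the control and ELF arms with 24 months of recruitment and 30 months of follow up are 22.5 and 39.1 years, respectively" are matched to 1000 patients, "giving a total of approximately 52 estimated events in the control arm" and 31 in the ELF arm. After the early close of recruitment, section 18.1 expects about 700 patients and roughly 80% power after five further years.

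**The concern.** The event trigger and the calendar date are offered as the same moment, but under the protocol's rates they are about two years apart. A committee that follows the date looks at a small fraction of the information; one that follows the event count waits until mid-2015. The protocol does not say which governs. Anyone who sets an interim boundary from the words in 19.1 would also start from the wrong information fraction.

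The level compounds this. As written, the formal interim and the five-year final analysis are both tested at 5%. At about 21 events such a test has little power, and a result that crossed would almost certainly overstate the effect, while the overall false-positive rate would exceed the nominal 5%.

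**Working it through.** **Inputs.** Medians of 22.5 years (270 months) and 39.1 years (469.2 months), section 18.1. Allocation 1:1, section 6.2. About 700 patients, sections 8.1 and 18.1. Accrual of 24 months, sections 18.1 and 18.2. Randomisation closes 30 April 2013, section 6.2. Interim at about month 27, section 19.1. Final follow-up of 69 months, section 18.1. Assumptions: uniform accrual, constant hazards, no dropout.

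**Formula.** With hazard λ, accrual a and minimum follow-up f, P(event) = 1 − [exp(−λf) − exp(−λ(a+f))]/(λa). Hazards per month are ln2/270 = 0.002567 (control) and ln2/469.2 = 0.001477 (ELF), so the hazard ratio is 0.575. Power for d events (Schoenfeld) is Φ(|ln HR|·√d/2 − 1.96).

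**Reproducing the protocol (a = 24).**

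| Patients | f (months) | Events, control + ELF | Power | Protocol states |
|---|---|---|---|---|
| 1000 | 30 | 51.0 + 30.1 = 81.1 | 70.1% | 52 + 31 = 83; 70% |
| 1000 | 69 | 93.8 + 56.4 = 150.2 | 92.3% | just over 90% |
| 700 | 69 | 65.7 + 39.5 = 105.1 | 80.9% | about 80% |

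The model returns the protocol's own figures, so it can be used for the interim.

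**Events at the interim.** Month 27 is a = 24 and f = 3, so P = 0.0376 (control) and 0.0219 (ELF). With 350 per arm that is 13.2 + 7.7 = 20.8 events. Uniform accrual over the whole 27 months gives 18.7; a month more of follow-up (f = 4) gives 22.2.

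**As a fraction of the expected events.**

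| Total used | Events | 20.8 as a fraction |
|---|---|---|
| Five-year final, 700 patients | 105.1 | 20% |
| Printed total, 1000 patients at 30 months | 83 | 25% |
| 30 months, 700 patients | 56.8 | 37% |
| July 2014, 700 patients (f = 15) | 37.1 | 56% |

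Half of 105.1 is 52.6 events, expected at about month 51. Half of 83 is 41.5, expected at about month 42. With recruitment starting about April 2011 (July 2013 less 27 months), month 51 is mid-2015.

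**Sensitivity to accrual.** If all 700 had entered on the first day and been followed for 27 months, the count would be 23.4 + 13.7 = 37.1, still short of 41.5 and 52.6. That extreme would pass half of the 30-month total (28.4), but it contradicts the stated recruitment. On the 1000-patient plan, month 27 gives 29.7 events, or 36% of 83.

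**What 20.8 events can show.** Power at 5% is Φ(0.553 × √20.8/2 − 1.96), about 24%. To reach p<0.05 the observed hazard ratio must be below about exp(−2 × 1.96/√20.8) = 0.42, well beyond the planned 0.575.

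**Type I error.** With interim information t = 20.8/105.1 = 0.198, the two test statistics have correlation √t = 0.445. Integrating the bivariate normal, the chance that either exceeds 1.96 in absolute value is 9.2%. With p<0.001 at the interim (|Z| > 3.29) and 1.96 at the final, it is 5.07%.

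**The case against.** Four points can be made in defence.

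*The denominator is undefined.* Section 19.1 does not say which expected total it means, and 20.8 is 56% of the 37.1 events expected by July 2014, the next formal analysis. A reader might infer that half can never be present in summer 2013; that is too strong. But the protocol prints no July 2014 total, section 18.1 says major liver events will not be reported within the Programme, and section 19.1 names the five-year analysis as final for this endpoint. The July 2014 reading does not rescue the sentence.

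*Boundaries belong in the SAP or the committee's terms of reference.* This stands as far as it goes: a missing boundary would be no finding. The difficulty is that section 19.2 states a level for all analyses, which a boundary elsewhere would contradict.

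*The interim may not be a decision test.* The protocol states no efficacy stopping rule, the report goes to the committee in confidence, and randomisation is due to close before the interim. This stands, and it limits the harm. The inflation arises only if an interim p<0.05 would count as a positive result.

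*July 2014 and the process outcomes.* A reader might count July 2014 as a third test of the primary endpoint and quote a larger error. The protocol does not plan one: there is a single interim on this endpoint, and section 18.1 ties July 2014 to the process outcomes. Nor can an error rate for those outcomes be built on 40% information, because the 40% in section 18.1 is interim power.

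**Conclusion.** The point holds in two parts.

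First, pairing half the expected events with summer 2013 is inconsistent with the protocol's own rates on the five-year, 30-month and printed totals; the expected share of the final events is about 20%. This rests on uniform accrual and constant hazards. Dropout would lower the count. Patients enrolled before version 5.0, if included, would raise it; the protocol gives no number for them.

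Second, read as written, the 5% level gives a type I error of about 9.2% over the interim and final analyses. That is conditional on testing the interim at 5% and treating significance as a positive finding, and an unseen SAP may already prevent it.

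This should be fixed, but it is not critical: it concerns one confidential look after recruitment closes, and the sample size and the definition of the primary analysis are untouched.

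**What to change.** In section 19.1, either replace half with the expected fraction (about 20% of the events at the five-year final analysis), or define the interim by an event count and let the date follow. In either case, name the total that the fraction refers to.

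In section 19.2, state that the two-sided 5% level applies to the final analysis of each outcome: five years for the primary endpoint, July 2014 for the process outcomes. State that the summer 2013 interim uses a stringent level such as p<0.001, and make this agree with any boundary in the SAP or the monitoring committee's terms of reference.

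The cost is two or three sentences. For the primary endpoint, overall error becomes about 5.1%, and because the final test stays at 1.96 the loss of power is negligible.
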